6.2 Methods of minimising bias

6.2.1 Randomisation

The randomisation is done by block randomisation with a block size of 2 patients. This is done to ensure the same number of patients in each of the two possible sequences.

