	 The detection of the receptive fields is planned as follows: 1. performed by two specifically trained testers 2. performed through tactile stimulation of the skin surface with a brush (mild toothbrush or similar) 				
	 the receptive fields are determined through the dialogue with the participant. Here he can signal the presence of a receptive field with the word "Yes". Important in this setup is that the participant does not look at the inspected site or the tester. 				
	 the receptive fields are drawn on to the skin with a commercial eveloper papel. 				
	 the drawn receptive fields are photographed from different locations under standardized conditions (distance and angle) 				

 this photo is imported in the program Photoshop (Adobe Photoshop Version 2017.1.1) where the respective area and position can be determined.
This testing Phase consists of 7 meetings of approximatively one hour. Therefore, the expenditure of time is of approximatively 7 hours over one month.
Phantom Stimulator:
Participants qualifying for the Phantom Stimulator are tested within 1 week after day 31. These tests are performed on one single half-day. Therefore, the expenditure of time for this phase is of approximatively 4 hours. The "Phantom Stimulator is worn for approximatively 3 hours during that phase.
 This day is planned as follows: -first (for familiarization): Walking for 1000 Steps with a step counter, questionnaire and 10 runs of gait analysis -second: The Phantom Stimulator (Cort X Sensorics, Spaichingen, Germany) will be installed -third: Participants will perform A or B in a randomized and balanced order: A. walking with the functioning (ON) Phantom Stimulator (1000 steps), questionnaire and 10 runs of gait analysis B. walking with the unfunctional (OFF) Phantom Stimulator (1000 steps), questionnaire and 10 runs of gait analysis
 For gait analysis, subjects will be walking in maximally possible self-selected speed for 10 runs (both directions are analyzed). The recorded parameters during the gait analysis are: Step width Step length Ground contact time Cadence Walking speed
The 1000 steps during the familiarization and testing phases are recorded/controlled through a pedometer (Omron Walking Style One 2.0, Mannheim, Germany).

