6. STUDY DESIGN

6.1 General study design and justification of design

The study with lower limb amputees is divided in two main parts and should incorporate 31 subjects.

The first part lasting 31 days, analyses the position and size of the receptive fields in a purely descriptive manner. Therefore, no randomisation, blinding or control group is needed.

The second part lasting 1 half-day, analyses the acute effect of a stimulation system (Phantom Stimulator, Cort X Sensorics, Spaichingen, Germany) on selected gait parameters and phantom sensations. Here the participants are randomized into two groups (AB or BA). As the design is a crossover, every subject serves as its own control and are single-blinded (unblinded investigators).

A schematic diagram can be found under 9.1 Study Flowchart.

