7.3 Assignment to study groups

The participants are assigned into the 2 possible sequences of the second part of the study in randomised order by block randomisation with a block size of 2 patients. This randomisation is performed by the principal investigator as soon as two patients are available. These are then randomized with the computer program Excel.

After this process, the assigned sequence is communicated to the responsible investigator for the patient and marked on the CRF. The patient is unaware of the study sequence until the study is terminated completely.

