9.3.8 Meeting 7 (day 31, 1h)

• detection of the receptive fields at the same time of day as on day 1 by the same tester as on day 1

9.3.9 Meeting 8 (second part of the study, done in 1 single half-day, 4h)

- **Phase 1:** Familiarization (1000 steps, questionnaire and gait analysis)
- **Phase 2:** Fitting of System and randomization
- Phase 3: AB or BA
 - A. walking with the functioning (ON) Phantom Stimulator (1000 steps), questionnaire and 10 runs of gait analysis
 - B. walking with the unfunctional (OFF) Phantom Stimulator (1000 steps), questionnaire and 10 runs of gait analysis

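### Part 2 order is drawn in fixed blocks of 2 by a principal investigator, with no concealment step described, and sections 7.3 and 9.3.9 disagree on when the draw takes place

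*Combined protocol and SAP*

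**What the plan says.** Part 2 compares the stimulator switched on (A) with the stimulator switched off (B) in the same patients, in the order AB or BA. Section 6.1 describes it as single-blind, with investigators who are not blinded.

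On the draw, section 6.2.1 states: "The randomisation is done by block randomisation with a block size of 2 patients". The reason given is: "This is done to ensure the same number of patients in each of the two possible sequences". Section 7.3 adds: "This randomisation is performed by the principal investigator as soon as two patients are available", and "These are then randomized with the computer program Excel". Afterwards, "the assigned sequence is communicated to the responsible investigator for the patient and marked on the CRF".

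Section 9.3.9 puts the draw elsewhere. It lists it as Phase 2 of the individual patient's meeting 8, after familiarisation: "Fitting of System and randomization". The synopsis limits when that meeting can occur: "Participants qualifying for the Phantom Stimulator are tested within 1 week after day 31".

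The sealed envelopes in section 6.3 hold codes for unblinding. Section 11.4.3 gives the A versus B evaluation to the principal investigators. The protocol describes no pre-generated list, draw log or independent list holder, and no rule for a last patient without a partner.

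**The concern.** In a two-period crossover, randomising the order protects the A versus B comparison from changes between the first and second randomised walk. Here each patient walks 1000 steps, fills in the questionnaire and does 10 gait runs at the fastest self-selected speed, three times in one half-day, so some fatigue is plausible.

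A shift common to all patients cancels when the two sequences are equal in size. A shift that differs between patients cancels on average only if nobody can influence who goes first with A. If staff know or can choose the order, several decisions may come to depend on it, even without intent: who takes which slot in a pair, whether a patient enters part 2, and whether a patient is withdrawn and the data kept (sections 7.4, 8.4 and 8.5 leave discretion). Any resulting difference in fatigue between the AB and BA groups would look like a device effect.

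**Working it through.** The plan states no figure on this point, so there is none to reproduce.

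**Inputs.** Block size 2 (6.2.1); two sequences in equal numbers (6.2.1); draw by a principal investigator once two patients are available (7.3), or at the patient's own meeting 8 (9.3.9); meeting 8 within 1 week after day 31 (synopsis).

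**Step 1: patients randomised singly, as 9.3.9 implies.** A block of 2 is AB-BA or BA-AB. The first allocation is guessed correctly with probability 1/2; the second is the complement and is certain.

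- Share determined: 1/2 = 50%.
- Expected correct guesses: (0.5 + 1)/2 = 75%.

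For comparison, a known block of 4 has 6 arrangements and 24 allocations. Two arrangements (both of one kind, then both of the other) have 2 forced allocations each and four have 1 each: 8/24 = 33.3%. Guessing the under-represented sequence is right 2 × 2.5 + 4 × 3 = 17 times in 24, or 70.8%. A known block of 6 gives 25.0% and 68.3%.

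**Step 2: the pair drawn jointly, as 7.3 states.** Both patients are identified before either sequence exists. At entry, 0% is determined and guesses are right 50% of the time. After the draw both orders are known, so the second patient's order is known before that patient's familiarisation, fitting and intensity setting. With one unlogged Excel draw for two known patients, nothing described would show whether it was repeated or which patient was put in which slot.

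**Step 3: can the joint draw be kept up?** The synopsis dates (24.10.2017 to 08.05.2018) span 196 days, or 28 weeks; 31/28 = 1.11 patients per week. If the last date means completion after about 5 weeks, this is 31/23 = 1.35 per week. Assume random arrivals and that 50% to 100% qualify for part 2 (neither is in the documents). The chance that no second patient qualifies within 7 days then runs from exp(-1.35) = 26% to exp(-1.11 × 0.5) = 57%. So the one-week window and the wait for a partner could often conflict, and staff would have to draw before day-31 eligibility is settled or randomise singly.

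**Step 4: route to bias.** Let τ be the A minus B effect and π a patient's change from the first to the second randomised walk. An AB patient yields τ - π and a BA patient τ + π. With equal groups the mean is τ + (π_BA - π_AB)/2, where π_BA and π_AB are group means. A common π cancels; a difference between the groups does not.

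For scale only, assume that π for walking speed is normally distributed between patients with SD 0.05 to 0.10 m/s (not in the documents). If the patient with the larger decline were always placed in AB, the bias would be 0.564 × SD = 0.028 to 0.056 m/s. If this happened in 25% of pairs, it would be 0.007 to 0.014 m/s. These figures assume that the person steering always recognises the larger decliner beforehand, so they are upper bounds for each share of pairs steered.

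**The case against.** The strongest reply is that 7.3 is the only section that describes the mechanism, and it has both patients in hand before the draw. A reader might infer that the second sequence in every pair is known in advance. Under 7.3 that is not so at entry; it follows only if the short entry in 9.3.9 means separate draws. This part of the reply stands, and the 50% and 75% figures belong to the single-draw case alone.

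Other parts also stand:

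- Randomised order is not the only safeguard against period effects. A full familiarisation bout comes first, and forced AB/BA balance cancels a common shift.
- Part 2 entry rests on amputation level and on fields that are drawn and photographed, which limits discretion. Devices are ordered at inclusion into part 2 (8.8). With single draws, only the second patient of a pair could be admitted with the order known.
- Unblinded staff could withdraw a patient after allocation under any scheme.
- Knowing the order adds little to assessment bias, because staff already know whether the device is on.
- Nothing shows that anyone could tell beforehand which patient will tire more.

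The reply does not remove the core of the point. The two sections conflict on timing, the role that draws is also the role that analyses, and under neither reading is the order held back until the patient's pre-allocation steps are complete.

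**Conclusion.** The point holds as a cheap improvement to a secondary, within-patient comparison. Fixed pairs known to study staff, an unlogged draw by a principal investigator, unblinded investigators and no described concealment leave the order open to foreknowledge (single draws) or to choice (joint draw). Bias can enter only through differential period effects or selective entry or exclusion. It is probably small; the m/s figures are illustrations resting on an assumed SD and perfect steering.

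Two further inferences are not supported. The block size is known to staff but is not by plan public: section 13 intends no public access to the full protocol. Nor do the documents establish that one person maps the fields, draws, runs meeting 8 and analyses. Section 7.3 separates the principal investigator from the patient's responsible investigator, and names and parts of section 1 are not available for review.

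**What to change.** Reconcile 7.3 with 9.3.9, and in 6.2.1 and 7.3 replace the pairwise draw with one list fixed before the first part 2 patient:

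- Use varying block sizes (for example 4 and 6) that are not disclosed to investigators.
- Have an existing employee who neither runs meeting 8 nor analyses the data prepare the list, save it as fixed values, and place each sequence in a sequentially numbered, sealed, opaque envelope.
- Open each envelope only at that patient's meeting 8, after eligibility, familiarisation, fitting and intensity setting are recorded. Note the time of opening on the CRF.

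This also removes the wait for a partner and covers an odd last patient. Varying blocks alone add little: in simulation with 20 patients, correct guesses fall from 75% to about 68% with blocks of 4 and 6. Most of the gain comes from the independent holder and the late opening.

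**Cost.** A wording change and about an hour's preparation. The sequences may end unequal, by at most 3 with blocks of 4 and 6. Relative efficiency is 4ab/n², where a and b are the two group sizes. At an assumed n = 20 split 11 to 9 it is 396/400 = 0.990; at n = 12 split 7 to 5 it is 140/144 = 0.972. These values assume that the effect is estimated by averaging the two sequence means. A plain mean over all patients would keep 2/20 = 10% or 2/12 = 17% of any common period shift, so section 11.4.3 should specify the former.

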6.2.2 Blinding procedures

The blinding of the participants is ensured as there is no visible difference between the two groups as well as through standardised questions and talking patterns of the investigators so not to reveal any relevant information.

6.2.3 Other methods of minimising bias

As other methods to minimise bias we use all well-established and validated tests and measurement methods in the gait analysis. Further we analyse the selected method of receptive field detection on intra-/intertester reliability.

6.3 Unblinding Procedures (Code break)

The codes for the unblinding procedures are stored in sealed envelopes which can be opened only by [name] or [name].

This procedure can take place in case of suspension/exclusion from the study, premature study termination, explicit requests from part of the CC or in case of individual analysation of the data because of health issues or threats to the participant.

7. STUDY POPULATION

7.1 Eligibility criteria

Participants fulfilling all the following inclusion criteria are eligible for the first part of the study:

- Informed Consent as documented by signature (Appendix Informed Consent Form)
- Lower limb amputation
- Legal age, capable of judgement

Participants fulfilling all the following inclusion criteria are eligible for the second part of the study:

- Lower limb amputation below/distal of the knee
- Presence of receptive fields for heel and forefoot at day 31 of the first part of the study

The presence of any one of the following exclusion criteria will lead to exclusion of the participant from the entire study:

- With history or suspect of non-compliance, drug or alcohol abuse
- Inability to follow the procedures of the study, e.g. due to language problems, psychological disorders, dementia, etc. of the participant
- Participation in another study with investigational drug within the 30 days preceding and during the present study
- Previous enrolment into the current study
- Enrolment of the investigator, his/her family members, employees and other dependent persons

The presence of any one of the following exclusion criteria will lead to exclusion of the participant from the second part of the study:

- Contraindications to the product under investigation (skin irritability or allergy to electrode glue)
- Women who are pregnant or breast feeding
- Intention to become pregnant during the study
- Implanted devices as pacemakers or defibrillators

7.2 Recruitment and screening

The study participants are preselected through a database of the Rehaklinik Bellikon and run per all in- and exclusion criteria. As a second step, the selected patients are contacted via E-Mail or personally if stationary at the Rehaklinik Bellikon. A pregnancy test is also conducted.

The preselection can be performed by every employee of the Rehaklinik Bellikon as he/she must have access to the patient information program. The second step of the contact via E-Mail, is performed through a separately created E-Mail address ([contact]) and can therefore be performed by authorised personnel only ([name] and [name]). Also, the personal contact is performed directly by one of the investigators ([name] and [name]).

7.3 Assignment to study groups

The participants are assigned into the 2 possible sequences of the second part of the study in randomised order by block randomisation with a block size of 2 patients. This randomisation is performed by the principal investigator as soon as two patients are available. These are then randomized with the computer program Excel.

After this process, the assigned sequence is communicated to the responsible investigator for the patient and marked on the CRF. The patient is unaware of the study sequence until the study is terminated completely.

7.4 Criteria for withdrawal / discontinuation of participants

Participants can be withdrawn from the Study in case of development of one of the exclusion criteria during the intervention, the informed consent is withdrawn, in case of non-compliance or safety concerns for the patient.

The withdrawn participants do not have to be replaced.

If the participant withdrawals from the study, his/her data must be anonymized at the end of the study. This anonymization is not done if the participant gives his/her explicit consent.

For the protection of the withdrawn participant he/her has to be provided follow-up care.

8. STUDY INTERVENTION

8.1 Identity of Investigational Products

8.1.1 Experimental Intervention

The investigated product is the Phantom Stimulator (Cort X Sensorics, Spaichingen, Germany). We obtain it directly from the developers ([name], [name]. [name]). It is composed of a sensory insole (pressure) connected to a plastic box (black/white), which is than connected to conventional electrode patches. This sensory insole is placed in the shoe, the box on the prosthesis shaft and the electrodes are placed on the receptive fields for forefoot and heel (same side as amputation).

There is no deviation from the intended use of the commercial product.

8.1.2 Control Intervention

Same as 8.1.1 Experimental Intervention. Only difference is that during the placebo phase, the system is unfunctional (not activated).

8.1.3 Packaging, Labelling and Supply (re-supply)

The system is packaged in a white carton box and except of the name, not labelled. The packaging also contains an operating instruction.

The re-supply, if further material is needed (extension cables, ...), is organised directly through the developers by the Rehaklinik Bellikon.

No deviation from the commercially available product is planned.

8.1.4 Storage Conditions

The devices are stored in a limited access storage room at climatized room temperatures of ca. 22°C and as in the box, with no exposure to sunlight. Once the products are in the hands of the participants they are informed to treat the product as described in the product information sheet.

These conditions are all according to standard procedures.

8.2 Administration of experimental and control interventions

8.2.1 Experimental Intervention

The experimental intervention concerns only the second part of the study. In the first part, a purely descriptive evaluation of the size and position of the receptive fields over the timespan of one month (31 days) is performed.

During the second part of the study, which is performed in one day, the certified medical device Phantom Stimulator (Cort X Sensorics, Spaichingen, Germany) is tested upon its effects on selected gait parameters and phantom sensations.

During the experimental intervention, the participants are setup with the device and are given an instruction. Further they are asked to walk 1000 steps with the functional device and to perform a gait analysis.

The time spent by the participants with the functional device is therefore restricted to 1000 steps and 10 times 10 meters of gait analysis.

Information on the medical device is given in section 8.1 and in the attached user manual.

8.2.2 Control Intervention

Also, the control intervention applies only for the second part of the study.

The control intervention consists of performing 1000 steps and a gait analysis under the same conditions as the experimental intervention, only difference being that the tested medical device is turned off during this period.

Therefore, also in the control intervention, the time spent by the participants is restricted to 1000 steps and 10 times 10 meters of gait analysis.

8.3 Dose / Device modifications

The only criteria for changing the dose or routine of the intervention are:

- the malfunctioning of a device which needs repair work
- if harm is done to the participants
- after explicit request of the participant (leads to exclusion from the study)
- if condition of the participant is drastically worsened by the medical device

8.4 Compliance with study intervention

To ensure compliance with the intervention we monitor the performed steps with a pedometer.

In case of non-compliance the participant is alerted once, if the non-compliance proceeds he/she is excluded from the study and the data, on an individual basis, kept and used or destroyed.

As in the different interventions during the study (detection and stimulation of the receptive fields) the participant is always in one to one support with the investigator, no additional strategies are required.

8.5 Data Collection and Follow-up for withdrawn participants

The data from withdrawn patients is analysed on an individual basis. Depending on the motive of withdrawal and the usefulness of the collected data, the material is kept and utilised in the study or destroyed.

Once a participant has withdrawn from the study, he has no follow up treatments or check-ups directly connected with the study.

8.6 Trial specific preventive measures

Medications or treatments not permitted during the study are:

- Drugs or psychopharmaceutic drugs altering the sensory perception other than normally taken
- Invasive treatments to the stump or the areas of the receptive fields
- Medication affecting the skin (tolerance of electrodes)
- Painkillers others than normally taken

8.7 Concomitant Interventions (treatments)

Permitted during the study are all form of usual medication the participants are/were taking

before the enrolment in the study if they don't fall under those listed in 8.6. Nevertheless, their use should be documented in the CRF.

The only medications having a potential impact on the study outcome are those concerning the phantom limb pain. In this case, we will perhaps expect a weaker improvement in phantom limb pain due to an already supressed starting point.

8.8 Study Drug / Medical Device Accountability

The devices are ordered directly from Cort X Sensorics (Spaichingen, Germany) at the moment of inclusion into the second part of the study of one of the participants. This must be done as the soles need to be personally adapted to the participant.

These devices are then shipped by postal service to the Rehaklinik Bellikon, where they are stored according to the regulations written in the user manual.

After completion of the study the used devices are returned to the manufacturer (Cort X Sensorics, Spaichingen, Germany).

